6.1. Study design

In this proof-of-concept study, sixteen young adult men (age: 28 ± 4) will be recruited in good physical condition. This will be a three-arm randomised cross-over study with a 1-week washout period between visits (**Figure 1**). Participants will be exercised following a 12-hour overnight fast (FAST) and exercised 90 minutes after a meal (FED) to test the temporal sensitivity of the loaded bone to absorbed nutrients. Participants will also attend a breakfast-only arm (without the exercise protocol). The meal will consist of 60% carbohydrate, 25% fat and 15% protein. The exercise will be a downhill running protocol adapted from previous studies in this area (Scott, 2012; Borer, 2019). Counterbalancing measures will be put in place to prevent and minimise order effects.

Participants will undergo a baseline assessment for health history (PAR-Q). Baseline measurements of weight, height, BMI and maximal oxygen uptake as well as baseline bone mineral density and body composition scans of participants will be performed with a dual energy X-ray absorptiometry (DXA) to characterise the study sample.

Figure 1: Study Design

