6.2 Power calculation

The primary outcome of this study is the difference in change in CTX concentration between the pre-exercise and 2-hour post-exercise timepoints between the fasted-exercised and fed-exercised arms.

Based on changes in CTX from a previous study (Scott et al., 2012), we designated 30% as a minimally significant difference and that 30% would be approximately 0.168 µg/l. We calculated a standard deviation of 0.2 µg/l based on results from our previous studies with serial measurements of CTX. To achieve 80% power for demonstrating this mean difference as statistically significant at the 2.5% two-sided level requires a total of 16 participants (including 2 additional participants for withdrawals). This sample size is in line with that of other studies in this area.

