5.4.2 Familiarisation

Once running speed has been determined, the participants will then be familiarised with the downhill running protocol to be used in the experimental visits. This familiarisation visit will expose the participant to the eccentric strain and the subsequent muscle damage associated with downhill running (Southall-Edwards, et al. 2022). As muscle damage can have a detrimental effect on markers of bone formation (Huang, et al. 2022), the prior exposure of the running protocol to the participants should blunt the muscle damage response in subsequent bouts of downhill running due to the repeated bout effect (Khassetarash, et al. 2022).

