6.9 Statistical analysis

Normality will be assumed if Shapiro-Wilk test is not statistically significant ($P > 0.05$). Where data is normally distributed, the data will be presented as mean and standard deviation (SD). Where data were not normally distributed, data will be presented as median and IQR.

Biochemical data will be analysed using a linear, mixed model (LMM), with factors 'condition' and 'time point' as fixed effects and 'participants' as a random, within-group effect. The assumptions of the LMM (homogeneity of variance and normality) will be investigated by examining the distribution of residuals and the pattern of residuals versus fitted values. Where non-normality or non-constant variance are observed, a log transformation will be applied to the data so that the assumptions are satisfied.

Where there is a significant main effect of *Time* but no significant *Condition* x *Time* interaction, each subsequent time point will be compared against 'Baseline' using a pooled mean from the three groups using Dunnett's test. If the *Condition* x *Time* interaction is significant, within each group, each time point will be compared against baseline using a Dunnett's test and groups will be compared to each other at all time points using the Student Newman-Keuls (SNK) test.

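### The crossover model adjusts for neither visit nor run order, and the readable text does not fix how often FAST precedes FED, so an order effect on the response may remain in the FAST versus FED contrast as bias or as lost precision

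*Combined protocol and SAP*

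**What the plan says.** Section 6.1 describes a randomised crossover of three conditions (FAST with exercise, FED with exercise, breakfast only) with one week between visits. On order it says: "Counterbalancing measures will be put in place to prevent and minimise order effects". Section 6.8 repeats that counterbalancing will be used to assign conditions at the second visit, and gives the remaining conditions to the third and fourth visits. The readable text of neither section lists the sequences, their number or the allocation ratio. Section 6.1 refers to Figure 1 for the design, and that figure is not shown in the copy reviewed.

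Section 5.4.2 (Familiarisation) gives one reason why order could matter. Downhill running causes muscle damage, which can affect bone formation markers, and the familiarisation run "should blunt the muscle damage response in subsequent bouts of downhill running due to the repeated bout effect".

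Section 6.9 fits a linear mixed model to all biochemical data with "factors 'condition' and 'time point' as fixed effects and 'participants' as a random, within-group effect". Time point is the sampling time within a visit. If the condition-by-time interaction is significant, conditions are compared with each other at every time point.

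Under section 6.2 the primary outcome is the FAST versus FED difference in CTX change from pre-exercise to 2 hours after exercise. The study "requires a total of 16 participants (including 2 additional participants for withdrawals").

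**The concern.** In a crossover, each participant's FAST-minus-FED difference includes any systematic difference between the earlier and the later of those two visits. Design can balance this out, or the model can adjust for it. Section 6.9 does not adjust, and the readable text does not show that the design balances the comparison that matters.

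The breakfast-only visit contains no run. For an effect tied to repeated running, the relevant balance is therefore FAST-first against FED-first, not equal use of each condition at each visit. A three-sequence Latin square uses each condition equally often at each visit and could fairly be called counterbalanced, yet it puts one exercise condition first in about two thirds of participants. With 16 participants, neither three nor six sequences can be filled equally, although an 8:8 order split is still possible.

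At stake is the contrast for which the trial was sized. Part of a run-order effect could be credited to feeding, or it could sit in the residual and widen the interval. Visit order will be known for every participant, so the adjustment needs no new data.

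**Working it through.** **Inputs from section 6.2.** Target difference: "30% would be approximately 0.168 µg/l". Variability: a "standard deviation of 0.2 µg/l", taken here as the SD of the paired FAST-minus-FED difference in change (assumption; the text does not say). Test: "statistically significant at the 2.5% two-sided level". Power: "To achieve 80% power for demonstrating this mean difference". Total 16, that is 14 plus 2.

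**The plan's own figure.** Paired normal approximation: n = [0.2 × (2.241 + 0.842) / 0.168]² = 13.47, rounded up to 14; plus 2 gives 16. The stated total reproduces, which supports reading 0.2 as a paired SD.

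**Bias formula.** Let o be the shift in CTX change at the second experimental run relative to the first. A FAST-first participant contributes −o to FAST minus FED, and a FED-first participant contributes +o. With no order term:

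bias = o × (n FED-first − n FAST-first) / n

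| Scheme | Order split | Absolute bias |
|---|---|---|
| Three-sequence Latin square, n = 16 | 11:5 or 10:6 | 6/16 = 0.375·o or 4/16 = 0.25·o |
| Six near-equal sequences, n = 16 | 9:7 at worst | 2/16 = 0.125·o |
| 8:8, two lost from one order | 8:6 | 2/14 = 1/7·o |
| 8:8, all complete | 8:8 | 0 |

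For comparison, if order were decided by a fair coin for each of 16 participants, the chance of exactly 8:8 would be 0.20 and of 11:5 or worse 0.21.

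**Size in µg/l.** The documents give no value for o, so it is set to 10%, 25%, 50% and 100% of 0.168 (assumption). With k = (difference in order counts)/n, the SD of the differences is √[0.2² + o²(1 − k²)]. Type I error and power come from the noncentral t distribution with n = 16.

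| o | Bias at 11:5 | Type I error at 11:5 (nominal 0.025) | SD at 8:8 | Power at 8:8 |
|---|---|---|---|---|
| 0 | 0 | 0.025 | 0.200 | 0.80 |
| 0.017 | 0.006 | 0.026 | 0.201 | 0.79 |
| 0.042 | 0.016 | 0.031 | 0.204 | 0.78 |
| 0.084 | 0.032 | 0.047 | 0.217 | 0.72 |
| 0.168 | 0.063 | 0.093 | 0.261 | 0.55 |

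At 8:8 the bias is zero and the type I error stays at 0.025.

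**Which term removes it.** A shift that raises or lowers every sample at a visit equally cancels from the within-visit change. Adding visit as a main effect to the section 6.9 model would therefore not adjust the primary contrast. In a model of the change score, a visit term alone still leaves 0.29·o to 0.35·o under the Latin square with n = 16, because visit number is not run number. A run-order term (first or second experimental run) reduces the bias to zero under any of the splits above. Its cost in standard error is 1/√(1 − k²): 1.033 at 10:6, 1.079 at 11:5, and none at 8:8.

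**The case against.** The strongest reply is that the design may already deal with this. The study is randomised and counterbalanced, has a washout, and includes a familiarisation run so that no experimental run is the first exposure. An 8:8 split is fully compatible with the text, and the sequences may be drawn in Figure 1. No section mentions a Latin square. All of this stands. A reader might infer that order effects do bias FAST versus FED; the documents do not support that, because the bias depends on a split that the readable text leaves open.

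A second reply is that the named mechanism concerns formation markers, while the primary outcome is a resorption marker. This also stands. A reader might infer that the protocol expects an order effect on CTX; it does not say so, and it describes prevention. The mechanism does bear on P1NP, which is measured and analysed with the same model.

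A third reply is that the effect may be small. With an 11:5 split and o at a quarter of the target, the type I error moves only from 0.025 to 0.031. That is fair, and any percentage of the target attached to this point rests on an assumed o.

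What the replies do not answer is that the model has no order term. An initially even split can be lost through the two withdrawals allowed for, and even an intact 8:8 split leaves the order effect in the residual.

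**Conclusion.** The point holds as a gap in the specification, not as a demonstrated bias. Order effects on the CTX response may remain in the primary contrast, and the readable plan cannot show otherwise. The bias is a fraction of an unknown run-order effect, and that fraction runs from zero to 0.375 depending on the order split. With an intact 8:8 split the only loss is precision: power falls from 0.80 to 0.78 if the effect is 0.042 µg/l and to 0.72 if it is 0.084 µg/l. These figures assume that 0.2 µg/l is the SD of the paired difference and that the order effect is a constant shift in the response. The Latin square is an illustration of what counterbalancing could mean, not a scheme in the plan. The change is worth making because it is cheap and uses information that will already exist.

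**What to change.** (a) In sections 6.1 and 6.8, state that participants are randomised over all six sequences, with 8 running FAST before FED and 8 the reverse.

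(b) In section 6.9, specify the analysis of the FAST versus FED change in CTX (pre-exercise to 2 hours post-exercise) with run order (first or second experimental run) as a covariate. Use either a change-score model or a run-order-by-time-point term in the mixed model.

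(c) In section 6.9, add visit (2, 3, 4) as a fixed effect for the between-condition comparisons of levels at each time point, where a visit-wide shift does not cancel.

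Cost: one degree of freedom for run order in a change-score model (more if crossed with time point) and two for visit. The run-order term adds about 3–8% to the standard error if the split is as unequal as in a Latin square, and nothing at 8:8. No visits, samples or participants are added. Fixing the adjustment before the data are seen also avoids a later choice between adjusted and unadjusted results.

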- To compare the effect of exercise on bone turnover markers before and after the meals following overnight fast in young adult male participants
- To assess the synergistic effects of feeding in addition to exercise on bone formation and resorption biomarkers in young adult male participants
- To determine the concurrent role of osteotropic hormone insulin in bone homeostasis in young adult male participants

Section 5: Background and rationale

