The complex and coordinated relationship between the endocrine regulation of energy metabolism, adipose tissue, and bone homeostasis has been studied extensively (De Paula et al., 2013). Concentrations of hormones, including insulin and amylin, change profoundly in anticipation of, during or after eating (preprandial, prandial, and postprandial responses). These hormones have potential anabolic effects on bone homeostasis, therefore, synergies between endocrine and mechanical effects could alter the bone turnover response to exercise.

The measurement of bone turnover markers, such as procollagen type 1 N-terminal propeptide (P1NP) and CTX, allow to assess the dynamic fluctuations in metabolic activity of bone (Delmas et al., 2006). Prolonged endurance exercise increases CTX (Guillemant et al., 2004; Hermann et al., 2007; Kerschan-Schindl et al., 2009; Maïmoun et al., 2006; Scott et al., 2010) but bone formation markers are largely unresponsive (Guillemant et al., 2004; Hermann et al., 2007; Maimoun et al., 2006; Scott et al., 2010). This suggests that prolonged exercise might result in a transient negative bone remodelling balance and this acute response may be implicated in changes in bone mineral density with repeated exercise over time in some sub-groups. However, the response of bone turnover markers to exercise is highly variable and appears to be modality-, intensity-, age- and sex-specific.

Feeding modulates the metabolic responses to prolonged exercise. The metabolic adaptations to fuel supply when fed and with fasting are well studied, however, there is limited consideration of the effect of these practices on other biological responses to exercise, such as bone metabolism. Fasting attenuates the circadian variation in CTX, a marker of bone resorption, whilst feeding suppresses resting CTX within 1-hour and concentrations are decreased by around 50% after 2–3 hours (Bjarnason et al., 2002; Henriksen et al., 2003; Holst et al., 2007). In contrast, and in line with the response to exercise, bone

formation is largely unresponsive to nutrient ingestion (Bjarnason et al., 2002; Henriksen et al., 2003; Holst et al., 2007). Concentrations of hormones including insulin and parathyroid hormone (PTH) change profoundly across pre-prandial, prandial, and postprandial states. These hormones have potential anabolic effects on bone homeostasis, therefore, synergies between endocrine and mechanical effects could alter the bone turnover response to exercise.

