6.4.3 Downhill running protocol

Participants will perform 45 min of treadmill running at 70% $VO_{2\max}$ at a -6% slope, one and half hours after a standardised breakfast (FED) or fasted (FAST). Downhill treadmill slope will increase Ground Reaction Forces (GRFs) relative to level walking (Gotschall and Kram, 2005).

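### Section 6.9 allows between-condition comparisons only after a significant Condition x Time interaction; otherwise it averages the resting control in with the two running conditions

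*Combined protocol and SAP*

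**What the plan says.** Section 6.1 defines two running conditions and a third without running: "Participants will also attend a breakfast-only arm (without the exercise protocol"). Section 6.8 has the breakfast-only visit sampled at the same times as the others.

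Section 6.9 fits a linear mixed model to each biochemical marker, with condition and time point as fixed effects and participant as random. The follow-up depends on the interaction test:

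- **Time significant, interaction not significant:** a Dunnett's test of every later sample against the baseline one, "using a pooled mean from the three groups".
- **Interaction significant:** within each condition, time points are compared with baseline by Dunnett's test, and "groups will be compared to each other at all time points using the Student Newman-Keuls (SNK) test".

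If neither Time nor the interaction is significant, no follow-up is specified. Nothing elsewhere in the document supplies a comparison of running with rest. Section 6.2 names FAST-exercised against FED-exercised, in CTX change from pre-exercise to 2 h post-exercise, as the primary outcome. Section 6.9 does not say that this contrast is reported regardless of the interaction test.

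**The concern.** Breakfast-only is the only condition that shows what a marker does over the morning without running. In the pooled branch it is averaged with the running conditions instead of being compared with them. The resulting change from baseline mixes four things: the running effect in two of three conditions, the meal effect in two of three, clock-time drift in all three, and the absence of running in one.

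A non-significant 8-df test in about 14 participants is weak evidence that the profiles are parallel. A marker with a real running response can therefore end up with a pooled time course as its only specified result. The same branch also omits the FAST versus FED comparison, which is the trial's main question. The first objective in Section 4, "To compare the effect of exercise on bone turnover markers before and after the meals", depends on comparisons between conditions that this branch does not make.

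**Working it through.** **Inputs from the documents.** There are three conditions, two with running (6.1), and five time points (6.8). The sample is 16, including 2 for withdrawals; the difference is 0.168 µg/l (30%), the SD 0.2 µg/l, with two-sided 2.5% and 80% power (6.2). Feeding lowers CTX by around 50% after 2-3 h (5.1).

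**Number of completers.** Reading 0.2 as the SD of the paired difference, n = ((2.241 + 0.842) x 0.2/0.168)² = 13.47, rounded up to 14; 14 + 2 = 16. The plan's figure is reproduced, so 14 completers are used below.

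**Interaction degrees of freedom.** (3 - 1) x (5 - 1) = 8.

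**Weights in the pooled mean.** Let running change a marker by E in FAST and in FED and by 0 at rest, with drift D in all three. The pooled change is (E + D + E + D + D)/3 = 2E/3 + D.

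- With D = 0, 0.168 µg/l becomes 0.112 µg/l.
- With unequal effects E and 0.5E, the pooled value is 0.50E against a running mean of 0.75E, which is again two-thirds.
- With an assumed D of 0.5 residual SD, pooled/true = 2/3 + 0.5/E (E in residual SDs). This is 2.33 at E = 0.3 and 1.17 at E = 1.0, so the running effect is overstated. Simulated averages within the branch, which add selection on significance, span 1.16 to 2.6.

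**A CTX illustration with the meal included.** The implied reference level is 0.168/0.30 = 0.56 µg/l, so a 50% fall is 0.28. Adding a running effect of +0.168 gives FAST +0.168, FED -0.112 and rest -0.280. The mean is -0.224/3 = -0.075, so the sign of the running effect is lost.

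**How often the branch is taken.** The documents give no residual SD for P1NP, cortisol, insulin or glucose, so effects are expressed in residual SDs. Simulation assumptions: 14 participants, 3 x 5 samples, participant random intercept, independent residuals, no drift, equal effects in both running conditions and none at rest, at 45 min only or at 15 and 45 min. The branch requires Time p < 0.05 with a non-significant interaction.

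| Effect (residual SD) | Pooled branch taken | Mean pooled estimate / true effect |
|---|---|---|
| 0.3-0.5 | 11-35% | 0.90-1.33 |
| 0.8-1.0 | 37-51% | 0.67-0.77 |
| 1.5 | 4-17% | about 2/3 |
| 2.0 | 0-1% | about 2/3 |

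At 0.3-0.5 SD the ratio exceeds 2/3 because the branch selects trials in which Time happened to be significant. At 0.8-1.0 SD the interaction is detected in only 28-62% of trials.

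**On the CTX scale.** For 0.168 µg/l at 2 h only, the interaction test has power 92%, 59% or 30% for an assumed residual SD of 0.10, 0.141 or 0.20 (0.2 read as the SD of the paired difference in change, of one change, or of one value). If the meal effect of 0.28 is present from the pre-exercise sample onward, it alone makes the interaction significant in about 77% to more than 99% of trials over the same SDs.

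**The case against.** **Following up a Time main effect when the interaction is non-significant is conventional, and 6.9 never calls the result an exercise effect.** Both points are correct. The defect is a missing contrast and a gate in front of it, not a biased estimate of a declared estimand. If the interaction is truly absent, running and rest run in parallel and there is no exercise effect to dilute. But non-significance here does not establish that, and a time course shared by running and rest is not an exercise response either.

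**The Condition main effect could serve as the comparison.** It averages over all five samples, two of them taken before running, and 6.9 specifies no follow-up to it.

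**A reader might infer that exercise effects will generally be reported at two-thirds size.** This does not hold. Two-thirds is the weight in the mean. What the branch reports also depends on drift and on selection, and it can exceed the true effect.

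**A reader might infer that P1NP is the marker most exposed, because 5.1 says of exercise "but bone formation markers are largely unresponsive".** The branch also needs a significant Time effect. At 0.2-0.4 SD without drift, neither test is significant in about 65-86% of simulated trials, so no pooled comparison is made. An effect of 0.8-1.0 SD does not fit an unresponsive marker. Drift could bring P1NP into the branch, but the documents do not quantify it.

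**A reader might infer that the first objective asks for running versus rest.** Read in full, it mainly concerns exercise before versus after a meal.

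**Reach is limited.** When the interaction is significant, the SNK step compares all three conditions. That is likely for CTX, and this is a proof-of-concept study. This stands, and it limits the severity.

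**Conclusion.** The point holds as a flaw in the analysis rule. Without a significant interaction, 6.9 specifies no comparison between conditions, and its only follow-up is a three-condition mean that absorbs the resting control. The 2/3 weight on the mean running effect and the full weight on drift are exact. The branch frequencies and estimate ratios rest on assumed effect sizes in residual SDs, 14 completers and independent residuals; the no-drift figures also assume equal running effects. They show that the branch is common at moderate effects and rare at large ones, and that the error can go in either direction.

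The documents do not support a claim that the primary CTX result is generally compromised, since the expected meal effect usually opens the gate. Severity is minor to moderate, mainly for the secondary markers.

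**What to change.** In 6.9, remove the interaction test as a gate and delete the three-condition pooled comparison. From the same mixed model, report for every marker, whatever the interaction p-value and each with a confidence interval:

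1. FED-exercised minus breakfast-only, in change from the pre-exercise sample to 15 min, 45 min and 2 h post-exercise. Meal and clock times match, so this is the exercise effect in the fed state.
2. FAST minus FED, in change from the pre-exercise sample to the same times. For CTX at 2 h this is the primary contrast of 6.2.

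That makes 5 markers x 3 times x 2 contrasts = 30, of which one is primary. Label the other 29 secondary, with a stated multiplicity adjustment, or exploratory.

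Do not present a FAST+FED average against breakfast-only as an exercise effect. Breakfast-only is always fed and there is no fasted resting condition, so that contrast mixes meal with exercise.

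The cost is SAP wording only, with the same model, samples and assays. The intervals will be wider than for the pooled mean. With independent residuals of SD s and 14 completers, the standard error is s x √(4/14) = 0.53s, against s x √(2/42) = 0.22s for the three-condition change, a factor of √6 = 2.45. The narrower interval belongs to a quantity that does not answer the question.

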1.2 Sheffield Hallam project reference number: ER52048815

1.3 Protocol version number and date: 5.0, 30th June 2024

Section 2: Research question(s)

1. Does timing of feeding around a mechanical loading stimulus to the skeleton alter the response of bone turnover to exercise?

Section 3: Abstract

The benefits of increased human lifespan depend upon the duration of healthy, independent living; the health span. Bone-wasting disorders contribute significantly to loss of independence, frailty, and morbidity in older people. Therefore, there is an unmet need globally for lifestyle interventions to reduce the likelihood of bone fractures throughout the life-course and with ageing. Although many mechanisms are involved in disorders of bone loss, there is no single regulatory pathway and, therefore, there is no single treatment available to prevent their occurrence.

We have previously shown that in young 17-week-old mice, 16-hour fasting followed by reintroduction of food for 2 hours increased markedly the potency of mechanical loading, which mimics the effect of exercise, to induce new cortical bone formation (Samvelyan et al, 2021). Consistent with this finding, fasting, and re-feeding increased the response of bone to a loading stimulus that, alone, does not stimulate new bone formation in ad-lib fed mice. The hormones, including insulin, that change in response to timing of feeding have osteogenic effects that interact with loading-mediated effects. Our findings indicate associations between timing of food ingestion and bone adaptation to loading.

Our aim in these studies is to determine whether fasting/feeding interventions alter the effect of mechanical loading on bone anabolic activities and increase bone mass. Such non-pharmacological lifestyle interventions may benefit skeletal health of humans throughout life-course and in older age.

Section 4: Aims and objectives of the study

The overall aim of this study is to determine whether an adequate mechanical stimulus to the skeleton and the timing of feeding, could improve the balance of bone formation to bone resorption and alter bone turnover in young adults. The primary endpoint of this study is the change of the bone resorption biomarker C-terminal telopeptide of type-1 collagen (CTX-1) expression between pre-exercise and 2 hours following the exercise timepoints.

Objectives:

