6.8 Outcome measures and participant involvement at each visit

All participants will be required to attend the Advanced Wellbeing Research Centre (AWRC) on four separate occasions.

At the **familiarisation visit** each participant will give informed consent. Consenting participants will complete a PAR-Q, undergo a $VO_{2\text{max}}$ test, and DXA scan to measure baseline bone mineral density and body composition. Baseline anthropometric measures, including height, weight, and BMI will be taken. Participants will be asked to follow a standardised diet three days prior to their second study visit. Participants will also be asked to refrain from strenuous physical activity during this period and will be asked to record their food and drink consumption in a diet diary.

At the **second visit**, each participant will arrive after a 12-hour overnight fast.

Counterbalancing measures will be used to assign participants to either the FASTED-exercised, FED-exercised or breakfast only conditions. During the FED-exercised or breakfast only arms, a standardised breakfast will be given at 8.30am. Exercise in the FED condition will take place 1.5 hours after breakfast has been administered (10.00am). When in the fasted condition, participants will also begin exercise at 10.00am.

Blood samples will be taken by cannulation for bone turnover marker measurement and hormone measurement at baseline (8.30am), pre-exercise (immediately before exercise), 15 minutes during exercise, 45 minutes (immediately post-exercise) and 2 hours post-exercise. Timings will also be consistent in the breakfast-only arm.

At the **third and fourth visits**, following crossover periods, participants will be assigned to the alternative conditions and study measurements repeated as per second visit.

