6.8.1 Summary of participant involvement by study time point

Study Time Point	Familiarisation Visit	First Pre-trial stage (3 days before visit 2)	Visit 2	Second Pre- trial stage (3 days before visit 3)	Visit 3	Third Pre-trial stage (3 days before visit 3)	Visit 4
Activity							
Informed Consent	X						
Demographic data	X						
Anthropometry (Height, weight & BMI)	X						
PAR-Q	X						
DXA Scan (Hip, Spine and Body composition)	X						
VO2Max Measurement	X						
Downhill Running Familiarisation	X						
Diet Diary		X		X		X	
Refrain from vigorous physical activity		X		X		X	
Follow standardised dietary advice		X		X		X	
Breakfast only (no exercise) or FED- exercised or FASTED- exercised condition			X		X		X
Blood samples for biochemical measurements			X		X		X
Urine Samples			X		X		X
Participant expenses given (£100 gift voucher)							X

6.8.2 Summary of biochemical measurements by study visit time point (for both fasted and fed conditions)

Study Visit Time Point	Baseline (8.30am)	Immediately Pre-exercise (10.30am)	During Exercise (15-minutes)	Immediately Post-Exercise Completion (45-minutes)	2-hours Post-exercise
Biochemical measurement					
CTX	X	X	X	X	X
PINP	X	X	X	X	X
Glucose	X	X	X	X	X
Insulin	X	X	X	X	X
Cortisol	X	X	X	X	X

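### The analysis section never tests the contrast the trial was sized on: FAST versus FED difference in CTX change from pre-exercise to 2 h, at 2.5% two-sided

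*Combined protocol and SAP*

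**What the plan says.** Section 6.2 states: "The primary outcome of this study is the difference in change in CTX concentration between the pre-exercise and 2-hour post-exercise timepoints", compared between the two exercise arms, FAST and FED. It powers the trial for "demonstrating this mean difference as statistically significant at the 2.5% two-sided level". Section 4 names the same interval for CTX-1, "between pre-exercise and 2 hours following the exercise timepoints", without naming the arms.

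Section 6.9 sets one scheme for all biochemical data: a mixed model with condition and time point fixed and participant random, then a branch on the Condition x Time interaction.

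- Interaction not significant, Time significant: Dunnett tests of each later time against baseline, on the mean of all three conditions together.
- Interaction significant: "within each group, each time point will be compared against baseline" by Dunnett, and "groups will be compared to each other at all time points using the Student Newman-Keuls (SNK) test".

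Section 6.8 lists samples "at baseline (8.30am), pre-exercise (immediately before exercise), 15 minutes during exercise", then at 45 minutes and 2 hours after exercise. Baseline and pre-exercise are therefore separate samples, with breakfast between them in the fed arms. (The table in 6.8.2 has "Immediately Pre-exercise (10.30am" where 6.8 has 10.00am; the two need reconciling, but nothing below depends on it.)

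**The concern.** None of the tests in 6.9 is the sized contrast, and 6.9 does not mention the 2.5% level. This would matter less if the arms were alike just before exercise. By the protocol's own account they should not be: 6.8 puts breakfast 90 minutes before FED exercise, and 5.1 says feeding lowers resting CTX within an hour and by about half after 2-3 hours. A FAST-FED difference in level at 2 h is then not a difference in the response to exercise, which is the research question in Section 2. SNK at the pre-exercise sample would often show that a gap came first, but not whether it changed. If the interaction is not significant, FAST and FED are not compared at all.

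**Working it through.** **1. What 6.2 sized.** Inputs from 6.2: difference 0.168 µg/l, SD 0.2 µg/l, 2.5% two-sided, 80% power. Section 6.2 does not say what the SD describes; take it as the SD of the within-participant FAST-FED difference in change.

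n = [(2.2414 + 0.8416) × 0.2/0.168]² = 13.47, so 14; plus 2 = 16, as stated.

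Alternatives do not fit: a paired contrast at 5% two-sided gives 12 + 2 = 14, and two independent arms at 2.5% give 27 per arm. The design basis is one paired contrast at 2.5%.

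**2. The 6.9 tests against that contrast**, (2 h − pre-exercise) in FAST minus (2 h − pre-exercise) in FED:

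| Test in 6.9 | What it tests | Why it differs |
|---|---|---|
| Condition x Time | (3−1)(5−1) = 8 df | Contains the 1-df contrast but does not isolate it |
| Dunnett | Times against the 8.30am sample, within or pooled over conditions | Wrong reference sample; never FAST against FED |
| SNK | Levels at each time, only after a significant interaction | Not changes |

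**3. Illustration.** Assumptions not in the documents: independent residual SD 0.1 per sample, so the contrast SD is √(4 × 0.1²) = 0.2; visit SD 0 / 0.05 / 0.1; interaction and SNK at 5%, since 6.9 gives no level; direct contrast at 2.5%. Reference CTX is 0.168/0.30 = 0.56. The error term is that of the participant-only model in 6.9; n=14; 10,000 runs per scenario. SNK is FAST against FED and counts only after a significant interaction. Triplets follow the three visit SDs.

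| Pattern in both fed arms | True contrast (size) | Interaction significant, % | SNK significant, % | Paired t, % |
|---|---|---|---|---|
| 1. Lower by 0.168 from pre-exercise on | 0 | 91.8 / 84.5 / 53.5 | at 2 h 91 / 83 / 49; at pre-exercise and 2 h 90 / 81 / 45 | 2.3-2.7 |
| 2. Lower by 0.168 at pre-exercise, a further 0.168 at 2 h | 0.168 | 100 / 100 / 99.2 | at pre-exercise and 2 h 99 / 97 / 88 | 73 |
| 3a. Lower by 0.168 at pre-exercise only | 0.168 | 92.0 / 84.8 / 53.7 | at 2 h 2-3; at pre-exercise 92 / 84 / 52 | 72-73 |
| 3b. Lower by 0.168 until 45 min, level at 2 h | 0.168 | 98.9 / 97.6 / 84.0 | at 2 h 2-3; at pre-exercise 98 / 95 / 75 | 72-73 |

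Rows 1 and 2 give the same SNK picture, a gap at both times, although one effect is zero and the other is the planned size. In rows 3a and 3b SNK at 2 h misses a real effect. The interaction is non-significant despite a real effect in 8 / 15 / 46% (3a), 1 / 2 / 16% (3b) and under 1% (row 2). With FAST equal to FED and only the breakfast-only arm lower by 0.168 from 15 min on (visit SD 0), the interaction is significant in 98.9% and the contrast in 2.5%.

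At n=16 the pattern holds: row 1 gives SNK at both times in 95 / 89 / 57%, and row 3a a non-significant interaction in 4 / 9 / 35%.

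**4. How the contrast is tested also matters** (n=14):

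| Test of the contrast at 2.5% | Type I error, % | Power, % |
|---|---|---|
| Participant-only model (6.9) | 2.4 / 1.6 / 0.3 | 81 / 75 / 58 |
| Participant-by-visit model, independent residuals | 2.4-2.7 | about 81 |
| Paired t | 2.6-2.8 | 72-73 |

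Under AR(1) within-visit correlation of 0.3-0.8, rescaled to keep the contrast SD at 0.2, the participant-by-visit model that assumes independence has type I error 3.6-6.0%; the paired t test stays at 2.4-2.6%.

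**The case against.** Section 6.2 already fixes the arms, time points, sidedness and level, and the mixed model could estimate the contrast, so only the link to 6.9 is missing. That is a fair description of the gap, but an analyst who follows 6.9 to the letter still never computes the primary result. Adding it later would leave test and scale to be chosen after the data are seen.

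The simulation rests on undocumented variances and assumed time courses. That stands: at visit SD 0.1 with zero effect, SNK is significant at both times in 45% of trials, not most.

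The largest missed-comparison figures come mainly from the participant-only error term. That also stands. In row 3a at visit SD 0.1, a significant paired t result sits behind a non-significant interaction in 27% of trials (7.5% in row 3b). With a participant-by-visit error term the interaction is non-significant in about 8% of row 3a trials at every visit SD, and such hidden results fall to 2.3% (0.2% in row 3b). The larger figures are nevertheless those of the model 6.9 states.

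The paired t test is one choice among several: it uses no third-arm data, makes no period adjustment and has less power than a correctly specified mixed-model contrast. That is why a mixed-model contrast is an acceptable alternative.

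**Conclusion.** Section 6.9 is wrong as written and must be changed before the data are seen. The finding rests on the text of 6.2, 6.8 and 6.9, with high confidence. Under the stated assumptions the 2 h SNK comparison is positive in about half to nine-tenths of trials when the primary effect is zero, and in 2-3% when a real effect leaves the arms level at 2 h. Those sizes depend on the assumed residual SD, visit SD and meal pattern; the mismatch between the sections does not.

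**What to change.** Add one paragraph to 6.9:

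- Primary analysis: for CTX, (2 h minus pre-exercise) in FAST minus (2 h minus pre-exercise) in FED.
- Test: a paired t test on the within-participant differences in change. If a mixed-model contrast is preferred, add a participant-by-visit random effect and state the within-visit correlation structure.
- Report the estimate, 97.5% confidence interval and p-value against the 2.5% two-sided level, whatever the interaction shows.
- State the scale: µg/l as in 6.2 or, if the log transformation is applied, a ratio of fold changes. These differ: if both arms rise by 0.10 after a 30% meal drop, the difference in change is 0 but the ratio is (0.66/0.56)/(0.492/0.392) = 0.94; after a 50% drop it is 0.87.
- Label the interaction, Dunnett and SNK tests as secondary.

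Visits, samples and planned recruitment need not change, but there are costs. The 14 completers reach 80% only on the normal approximation (81.6%). Exact paired-t power is 72.3% at 14, 79.7% at 16 and 82.7% at 17, so 80% needs 17 completers; that shortfall should be accepted openly or addressed. On the log scale the 0.168 µg/l target no longer applies directly. A CTX level difference at 2 h could no longer be presented as the primary result.
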